9.3 Physical and Neurological Examination and Vital Signs

Physical and neurological examination findings will be listed by subject.

Summary statistics for change from baseline in vital signs, body weight, and waist circumference will be provided by treatment group.

In addition, the incidence of treatment-emergent PCR values identified using prospectively defined criteria in Appendix 2 for vital signs and body weight will be summarized by treatment group. Listing of PCRs by subject and by test will be provided.

9.4 12-Lead ECG

Summary statistics for change from baseline in ECG parameters will be provided by treatment and by visit.

In addition, the incidence of treatment-emergent potentially clinically relevant (PCR) values identified using prospectively defined criteria for ECG will be summarized by treatment group. Listing of PCRs by subject and by test will be provided.

For the analysis of QT and QTc, data from three consecutive complexes (representing three consecutive heart beats) will be measured to determine average values. The following QT corrections will be used for reporting purposes in the clinical study report:

- 1) QTcB is the length of the QT interval corrected for heart rate by the Bazett formula: $QTcB=QT/(RR)^{0.5}$ and
- 2) QTcF is the length of the QT interval corrected for heart rate by the Fridericia formula: $QTcF=QT/(RR)^{0.33}$
- 3) QTcN is the length of the QT interval corrected for heart rate by the FDA Neuropharm Division formula: $QTcN=QT/(RR)^{0.37}$

Categorical changes in ECG parameters during the double blind treatment period will be summarized based on the following criteria:

Categorical Change Criteria in QT/QTc Parameters		
Classification	Category	Criteria
QT	New Onset (≥ 450 Msec for men or ≥ 470 Msec for women)	New onset in QT means a subject who attains a cut off value during treatment period but not at baseline.
QTc *	New Onset (≥ 450 Msec for men or ≥ 470 Msec for women)	New onset in QTc means a subject who attains a cut-off value during treatment period but not at baseline.
	New Onset (≥ 450 Msec for men or ≥ 470 Msec for women) And $> 10\%$ Increase	New onset and $> 10\%$ increase in QTc means a subject who attains a cut off value and $> 10\%$ increase during treatment period but not at baseline
	New Onset (> 500 Msec)	New onset (> 500 msec) in QTc means a subject who attains a value > 500 msec during treatment period but not at baseline.
	Increase 30 - 60 Msec	Increase from baseline value > 30 and ≤ 60 msec in QTc
	Increase > 60 Msec	Increase from baseline value > 60 msec in QTc

* QTc categorical change criteria apply to QTcB, QTcF and QTcN.

[figure not shown]
9.5 Body Weight, Waist Circumference and Body Mass Index (BMI)

Analyses of body weight, waist circumference and BMI will be performed for the Safety Sample. Body mass index is defined as weight in kilograms divided by the square of height in meters. The mean change from baseline to Week 12 (OC) and the last visit in the double blind treatment period in body weight will be tabulated and analyzed using ANCOVA. The ANCOVA models will include the baseline as a covariate and the treatment group as fixed effect.

Percentages of subjects showing significant weight gain ($\geq 7\%$ increase in weight), as well as percentages of subjects showing significant weight loss ($\geq 7\%$ decrease in weight)

from baseline to Week 12 (OC and LOCF) will be analyzed using Cochran-Mantel-Haenszel (CMH) General Association Test.

9.6 CCI [REDACTED]

9.7 Mini-Mental State Examination (MMSE)

The mean changes from baseline to Week 12 (OC) and the last visit in the double blind treatment period in MMSE will be tabulated and analyzed by treatment group using ANCOVA. The ANCOVA model for the OC data set will include the baseline item score as covariate and treatment group as main effect. The ANCOVA model for last visit will include the baseline item score as covariate, and study center, treatment group as main effects. The analyses will be performed for Safety Sample.

9.8 CCI [REDACTED]

9.9 Concomitant Medications

Number and proportion of subjects taking concomitant medications prior to study therapy, during the double blind treatment period, and after study therapy are tabulated by drug classification using the WHO drug dictionary.

9.10 Extent of Exposure

The start date of double-blind study therapy - brexpiprazole or placebo - will be the first day of double-blind dosing. The number and percentage of subjects, who receive double-blind study medication, will be presented by week and by treatment group. Each dosing week will be based on the actual week; i.e., Day 1-7 in Week 1, Day 8-14 in Week 2, etc. This summary will be performed on the Safety Sample.

The number and percentage of completers will be presented by week and by treatment group.

The mean daily dosage will be summarized by week and treatment group using descriptive statistics. The mean daily dosage per subject per week will be determined for each week of the study. This will be calculated by dividing the sum of individual total doses by the number of days in the week interval. The summary will contain for each treatment group the number of subjects receiving double-blind study medication, and the mean and range of the mean daily dose for each week.

10 Conventions

10.1 Study Visit Windows

Study visit windows will be used to map visits using study day intervals. This visit window convention applies to tables and listings for all efficacy and safety scales. This derived study window variable will be named as WEEK and will be footnoted. In listings it will be listed along with the CRF study visit.

Table below shows classifications for study day intervals in the double-blind period. The variable “target day” is defined using the number of days since the start of double-blind dosing. The first day of double-blind dosing is defined as “Day 1”. If more than one observation falls within a particular study day interval, then the last observation within that interval is used. **cci**

CCI

Study Day and Visit Window

Week	Target Day ^a	Study Day Interval ^a
1	7	2-10
2	14	11-17
3	21	18-24
4	28	25-31
5	35	32-38
6	42	39-45
7	49	46-52
8	56	53-59
9	63	60-66
10	70	67-73
11	77	74-80
12	84	81-91 ^b

^a Relative to the first day of IMP in the double blind treatment period.

b CCI

S.

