Subjects will follow a titration schedule, depending upon their assigned treatment group, to gradually increase their dose to their assigned target dose.

Subjects unable to tolerate their assigned dose of brexpiprazole (or matching placebo) will be withdrawn from the trial. Down-titration is not allowed at any time during the study. If a subject is withdrawn, every effort will be made to complete all of the Week 12/Early Termination (ET) evaluations prior to administering any additional medications for the treatment of agitation or other prohibited medications.

Subjects will be evaluated at Baseline, Day 3, and Weeks 2, 4, 6, 8, 10, and 12 during the double-blind treatment period.

All attempts should be made to maintain the subjects' normal routine with regard to physician appointments. Individual circumstances that fall outside this general convention should be discussed with the medical monitor in order to determine appropriateness to

proceed. In addition, the subject's identified caregiver will be contacted by telephone at Weeks 3, 5, and 7 to assess compliance with IMP, confirm any changes to concomitant medications, and assure the subject's well-being. Trial-related efficacy and safety assessments will be performed as outlined in the study protocol.

Follow-up Period

All subjects, whether they complete the trial or are withdrawn prematurely for any reason, will be followed up for a safety evaluation 30 (+ 2) days after the last dose of the IMP during a clinic visit at either the investigator's site or residential facility, if applicable. If a clinic visit is not possible, the subject should be assessed by telephone contact with the subject and a caregiver. For all subjects who terminate early from the trial, all attempts will be made to collect mortality data by telephone contact with the subject's caregiver at Week 16.

Subjects who complete both the 12-week double-blind treatment period and the 30-day safety follow-up visit are eligible to enroll into Trial 331-13-211, which is a 2-month, observational, rollover trial to evaluate the safety of subjects with agitation associated with Alzheimer's disease who previously participated in Trial 331-12-283. For those subjects who plan to enroll into Trial 331-13-211, the 30-day safety follow-up visit for Trial 331-12-283 will occur as a clinic visit at either the investigator's site or residential facility, if applicable.

4 Sample Size and Power Justification

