5.2 Handling of Missing Data

The CMAI is utilized as the primary efficacy assessment of a subject's level of agitated behaviors. The CMAI consists of 29 items all rated on a 1 to 7 scale with 1 being the "best" rating and 7 being the "worst" rating. The CMAI Total Score is the sum of ratings for all 29 items. The possible total scores are from 29 to 203. The CMAI Total Score will be unevaluable if less than 24 of the 29 items are recorded. If 24 to 28 of the 29 items are recorded, the total score will be the mean of the recorded items multiplied by 29 and then rounded to the first decimal place.

CCI
[REDACTED]
[REDACTED]
[REDACTED]
[REDACTED]
[REDACTED]
[REDACTED]

The primary efficacy variable is the change from baseline to Week 12 in the CMAI total score.

In general, missing data will be handled by analysis of Mixed effect Model Repeat Measurement (MMRM) methodology based on observed-case (OC) data from protocol-specified visits in the ITT population under the assumption of missing at random (MAR).

The OC dataset consists of actual observations recorded at each visit during the double-blind acute treatment phase, and no missing data will be imputed.

CCI
[REDACTED]
[REDACTED]
[REDACTED]
[REDACTED]
[REDACTED]
[REDACTED]
[REDACTED]
[REDACTED]

6 Study Conduct

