8.1.1 Primary Efficacy Analysis

The primary endpoint will be analyzed using a mixed-effect model repeated measure (MMRM) model. The primary efficacy outcome measure is the mean change from baseline (Day 0 visit) to the end of the double-blind treatment period (Week 12 visit) in the CMAI total score. The primary statistical comparisons of interest are brexpiprazole 2 mg/day versus placebo and brexpiprazole 1 mg/day versus placebo. The null hypotheses of these comparisons are that there is no difference between the brexpiprazole treatment groups and placebo in change from baseline to endpoint in CMAI total score. To protect the experiment-wise 2-sided alpha level at 0.05 when making 2 comparisons of brexpiprazole doses versus placebo, the statistical testing will be carried out using a hierarchical testing procedure in the order of 1) comparison of 2 mg/day brexpiprazole versus placebo and 2) comparison of 1 mg/day brexpiprazole versus placebo. Thus, if the test yields a statistically significant result at 0.05 (2-sided) for the comparison of 2 mg/day brexpiprazole versus placebo, then the comparison of 1 mg/day brexpiprazole versus placebo will be tested at an alpha level of 0.05 (2-sided).

The primary analysis will be performed on the Efficacy Sample which includes all randomized subjects who took at least one dose of IMP in the double blind treatment period and who have both a baseline and at least one post-randomization CMAI Total Score during the double blind treatment period. The primary efficacy analysis will be performed by fitting a MMRM analysis with an unstructured (UN) variance covariance structure in which the change from the baseline in CMAI Total Score (Week 2, 4, 6, 8, 10, 12) will be the dependent variable based on the OC data set. The model will include fixed class-effect terms for treatment (1 mg/day, 2 mg/day, and placebo), trial center, visit week, and an interaction term of treatment by visit week and include the interaction term of baseline values of CMAI Total Score by visit week as covariates. The primary comparison between a brexpiprazole and the placebo arm at Week 12 will be estimated as the difference between Least Squares (LS) means from the interaction term of treatment by visit week utilizing the computing software SAS procedure PROC MIXED.

[figure not shown]
CCI

[figure not shown]

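### As far as the visible SAP shows, the day-based windows send early-termination CMAI scores in odd-week windows to weeks that the primary MMRM does not read

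*SAP*

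**What the plan says.** - **Windows (SAP 10.1).** Visits are assigned by study day: "Study visit windows will be used to map visits using study day intervals". The scope includes the CMAI: "This visit window convention applies to tables and listings for all efficacy and safety scales". The table runs without gaps from Week 1 (Days 2–10), through seven-day windows for Weeks 2 to 11, to Week 12 (Days 81–91). Ties are settled thus: "If more than one observation falls within a particular study day interval, then the last observation within that interval is used". The text directly after that sentence and footnote b to the Week 12 interval are redacted.
- **Primary model (SAP 8.1.1).** "the change from the baseline in CMAI Total Score (Week 2, 4, 6, 8, 10, 12) will be the dependent variable". No odd week appears.
- **Data used (SAP 5.2).** The MMRM assumes missing at random (MAR) and is "based on observed-case (OC) data from protocol-specified visits in the ITT population". On imputation the same section is explicit: "The OC dataset consists of actual observations recorded at each visit during the double-blind acute treatment phase, and no missing data will be imputed".
- **Schedule and withdrawal (SAP 3).** After baseline, subjects are evaluated on Day 3 and at the even weeks; Weeks 3, 5 and 7 are caregiver telephone calls. When a subject is withdrawn, "every effort will be made to complete all of the Week 12/Early Termination (ET) evaluations", before other agitation medication is given.
- **Efficacy Sample (SAP 5.1, 8.1.1).** Besides a dose of IMP and a baseline score, one post-baseline CMAI is enough, with no restriction on the week.

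**The concern.** The window table and the model's list of weeks do not match. After Day 3 no evaluation is scheduled in an odd week, so for a scale taken every two weeks the windows for Weeks 3, 5, 7, 9 and 11 can hold only early-termination assessments or scheduled visits well off target. The model reads none of these weeks, and no visible rule moves their contents to a week that it does read.

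The MMRM relies on MAR: dropout must be explained by the scores in the model. The early-termination CMAI is the score closest to the reason for leaving. If it is left out, dropout that the data could have explained becomes partly unexplained, and the Week 12 contrast can move if that process differs between arms. The SAP takes trouble to obtain this score, so data already collected would go unused. The Efficacy Sample count could also exceed the number of subjects who contribute to the primary analysis.

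**Working it through.** **1. The plan's own figure.** Effect 6.5, SD 16.5, two-sided 0.05, power 85% (SAP 4). Normal approximation: n = 2 × (1.960 + 1.036)² × 16.5² / 6.5² ≈ 116 per arm. The noncentral t gives 84.8% power at 116 and 85.1% at 117, so the stated 117 reproduces. This point does not affect it; the effect and SD serve only as a scale below.

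**2. Days in odd-week windows (table in 10.1).**
- Week 1: Days 2–10 = 9 days.
- Weeks 3, 5, 7, 9, 11: 5 × 7 = 35 days.
- Total: 9 + 35 = 44.
- Days before the Week 12 window: Days 2–80 = 79, so 44/79 = 55.7%.

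The share depends on the denominator: 44/82 = 53.7% for Days 2–83, 44/90 = 48.9% for the whole table, and 35/70 = 50.0% for Days 11–80. The excess over one half comes from the nine-day Week 1 window.

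**3. Three subjects traced through the visible rules.**
- Week 2 visit on Day 14, early termination on Day 26: the score maps to Week 4 and is used.
- Week 2 visit on Day 14, early termination on Day 21: the score maps to Week 3 and is not used; the model sees only Day 14.
- Early termination on Day 8 with no earlier CMAI: the score maps to Week 1. The subject is in the Efficacy Sample and has no row in the model.

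**4. How many scores (assumption).** The SAP gives no early-termination rate or timing. Assume 10–20% early termination, every such CMAI obtained, days spread evenly, and 396 (3 × 132) to about 420 subjects (both from SAP 4; the context of 420 is redacted). Low end: 396 × 0.10 × 44/90 = 19. High end: 420 × 0.20 × 44/79 = 47.

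**5. Effect on the Week 12 difference (simulation).**

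(a) Dropout driven by the score at exit, no added worsening, true effect 6.5, other inputs assumed. When the dependence on the exit score differed by arm, the windows as written were off by 0.3–0.5 points. Assigning the early-termination score to the next visit came within 0.1 of the full-data estimate. When the dependence was the same in both arms, the shift was near zero.

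(b) Dropout after a sudden worsening. 118 per arm (132 × 0.9 = 118.8), effect 6.5, Week 12 SD 16.5, worsening dropout 12% versus 6%, other dropout 6%, correlations and timing assumed, 2000 replicates:

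| Scenario | Windows as written | Score kept | Full data | Written vs kept |
|---|---|---|---|---|
| Placebo worsens more, 15 points | −6.88 | −7.20 | −7.42 | 0.32 |
| Drug worsens more, 15 points | −6.21 | −5.87 | −5.64 | 0.34 |
| Placebo worsens more, 20 points | −7.02 | −7.47 | −7.76 | 0.45 |
| Equal dropout | −6.47 | −6.47 | −6.46 | 0.00 |

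A second run of the three unequal scenarios (3000 replicates, its own assumed inputs) gave shifts of 0.39, 0.44 and 0.50. About 3 of 236 subjects had no row in the model.

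**6. Scale.** 0.3/6.5 = 5% and 0.5/6.5 = 8% of the planned effect. The standard error of a two-arm difference is about 16.5 × √(2/117) = 2.16, so the shift is 0.3/2.16 = 0.14 to 0.5/2.16 = 0.23 standard errors.

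**The case against.** **Redaction.** Text is blacked out exactly where an early-termination rule would normally stand: after the last-observation sentence and at footnote b in 10.1. Nothing is visible under 8.1.2 or 8.1.3. This stands. A reader might infer that the SAP discards these scores; the documents do not establish that, because redacted text is not missing text. Some visible features point the other way from a hidden rule: the interval table is printed complete, footnote b attaches only to Week 12, and 9.5 and 9.7 report Week 12 observed cases separately from the last visit. They suggest, but do not prove, that off-week final values stay out of the weekly data.

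**The rule may be deliberate.** Limiting the model to protocol-specified visits fits leaving off-schedule scores out, and moving a score to a later visit carries its own assumption. This stands in part. The visible text does not settle whether a Week 12/ET evaluation counts as protocol-specified, and the omission bears directly on the MAR assumption.

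**The simulation in 5(b) favours keeping the score by construction.** If the worsening lasts to Week 12, the full-data contrast itself moves away from 6.5. Measured against 6.5, the windows as written look closer (−6.88 versus −7.20). This is fair for 5(b), but 5(a) adds no worsening and still shows 0.3–0.5 points.

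**Days are not dropouts.** A reader might infer that over half of dropouts, or many of them, lose their exit score. The SAP has no figure for that; 56% is a share of days before the Week 12 window.

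**Conclusion.** The mismatch is real in the visible text. An early-termination CMAI in an odd-week window has no stated route into the primary MMRM, and a subject with only such a score would be in the Efficacy Sample without contributing. Whether this happens in practice depends on redacted text, so confidence is moderate.

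The likely consequence is modest: about 0.3–0.5 CMAI points on the Week 12 difference, in either direction. It arises only if dropout of roughly 10–20% per arm depends on the exit score differently by arm. With the same dependence in both arms it almost vanishes. The dropout rates, timing and correlations are assumptions. It would therefore go too far to infer that the primary result is biased, or biased in favour of the drug; the documents support neither. The point merits a clear rule before unblinding and does not undermine the design.

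**What to change.** Unless the redacted text already does so, state in 10.1 and 8.1.1 how early-termination CMAI scores enter the MMRM:

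- Assign an early-termination CMAI that falls in an odd-week window to the next scheduled visit: Days 2–10 to Week 2, 18–24 to Week 4, 32–38 to Week 6, 46–52 to Week 8, 60–66 to Week 10, 74–80 to Week 12.
- Keep scheduled visits at their nominal week. Simply merging each odd window into the next even one is not equivalent: a late Week 10 visit on Day 75 would then become Week 12.
- Keep any on-treatment limit that the SAP already applies, and the existing last-observation rule where two records share a week.
- Run the narrow windows as a sensitivity analysis.
- Report how many Efficacy Sample subjects supply no row to the primary model.

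The cost is a short SAP edit and one derivation change before unblinding. The downside is timing: a Day 18 score analysed at Week 4 (target Day 28) is placed 28 − 18 = 10 days late, and a Day 2 score at Week 2 (target Day 14) 14 − 2 = 12 days late. The sensitivity analysis shows whether that matters.

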10.2 Pooling of small centers

Primary efficacy analysis will be performed on the ITT Efficacy Sample which comprises those subjects in the Randomized Sample who have a baseline value and at least one post-randomization value for CMAI Total Score in the double blind treatment period.

CCI

10.3 Scales: Rules for Scoring and Handling of Missing Data

10.3.1 Cohen-Mansfield Agitation Inventory (CMAI)

The CMAI consists of 29 items all rated on a 1 to 7 scale with 1 being the “best” rating and 7 being the “worst” rating. The CMAI Total Score is the sum of ratings for all 29 items. The possible total scores are from 29 to 203. The CMAI Total Score will be unevaluable if less than 24 of the 29 items are recorded. If 24 to 28 of the 29 items are recorded, the total score will be the mean of the recorded items multiplied by 29 and then rounded to the first decimal place.

CCI [REDACTED]

[REDACTED]

[REDACTED]

[REDACTED]

[REDACTED]

[figure not shown]
[figure not shown]
[REDACTED]

.

10.3.2 Clinical Global Impression-Severity of Illness Scale (CGI-S)

The severity of agitation for each subject will be rated using the CGI-S. To perform this assessment, the investigator (or designee) will answer the following question:

“Considering your total clinical experience with this particular population, how mentally ill (as related to agitation) is the subject at this time?” Response choices are 0 = not assessed; 1 = normal, not at all ill; 2 = borderline mentally ill; 3 = mildly ill; 4 = moderately ill; 5 = markedly ill; 6 = severely ill; and 7 = among the most extremely ill subjects. The score 0 (= not assessed) will be set to missing. The CGI-S is therefore a 7-point scale from 1 through 7.

10.3.3 CCI**10.3.4 CCI****10.3.5 Neuro-psychiatric Inventory**

The NPI consists of 12 items. For each item there is a screening question to determine if the behavioral change is present (rated 1) or absent (rated 0). For each item there are three scores: frequency, severity, and caregiver distress (NPI/NPI-NH) or occupational disruptiveness (NPI-NH). Frequency is rated on a 1 to 4 scale, severity is rated on a 1 to 3 scale and the caregiver distress is rated on a 0 to 5 scale. The individual item score is calculated as presence x frequency x severity and has a range from 0 to 12. If presence is zero, the individual item score and caregiver distress score will be set to zero. For all items, low scores are 'better' than high scores.

The NPI Total Score is calculated by adding the individual item scores of the 12 items together. The possible total scores are from 0 to 144. The NPI Total Score will be

unevaluable if less than 10 of the 12 items are recorded. If 10 or 11 of the 12 items are available then the total score is the mean of the available scores times 12. All imputed scores are rounded to the first decimal place.

CCI

[figure not shown]

